**Question 2**

**What is your gender?**

- |                   |                          |
|-------------------|--------------------------|
| Female            |  |
| Male              |  |
| Non-binary        |  |
| Prefer not to say |  |

**Question 3**

**What is your ethnicity?**

- |  |                          |
|--|--------------------------|
| Asian or Asian British                     |  |
| Black, African, Caribbean or Black British |  |
| White                                      |  |
| Mixed or multiple ethnicities              |  |
| Other (please specify)                     |  |
| <hr/>                                      |                          |
| Prefer not to say                          |  |

**Question 4**

**Are you currently employed in, or have previously been employed in, a position with protected research time as part of your job plan?**

*(Please select all that apply)*

- | If yes:                                      | Current role             | Previous role            |
|---|--------------------------|--------------------------|
| Academic Foundation Programme                       |  |  |
| Academic Clinical Fellow                            |  |  |
| Academic Clinical Lecturer                          |  |  |
| Research Fellow                                     |  |  |
| Associate Principal Investigator (of another study) |  |  |
| Principal Investigator (of another study)           |  |  |

*If no:*

- |   |                          |
|---|--------------------------|
| No previous research experience   |  |
| Previous research experience but in my own time whilst not employed in a research role (i.e. recruiting patients, data collection, research publication, research presentation) |  |
| Other (please specify)  |  |
| <hr/>   |                          |

---

## SITE TEAM

**The following questions are about your experience of joining the study and the day-to-day running at your site.**

### **Question 5**

**How did you hear about the PIM-COVID study?**

*(Please select all that apply)*

- |  |                          |
|--|--------------------------|
| From the Senior PI                         |  |
| From the Trainee PI                        |  |
| From an ICU consultant (not the Senior PI) |  |
| TRIC network mailing list                  |  |
| Twitter                                    |  |
| Other (please specify)              |  |
- 

### **Question 6**

**What role did you have on the PIM-COVID delegation log?**

*(Please select one)*

- |                                    |                          |
|------------------------------------|--------------------------|
| Trainee PI                         |  |
| Senior PI                          |  |
| Sub-investigator / co-investigator |  |
| Not sure                           |  |

### **Question 7**

**Were you involved with the study set up at your hospital?**

- |     |                          |
|-----|--------------------------|
| Yes |  |
| No  |  |

*If you answered Yes to Question 7, please proceed to Question 8.*

*If you answered No to Question 7, please proceed to Question 9.*

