**Question 8**

To what extent do you agree with the following?

	Strongly disagree	Disagree	Neither agree nor disagree	Agree	Strongly agree
Setting up the study at my site was easy					
It was clear what was expected of the site team					
The site team were well supported by the central study team					
I knew who to contact if advice was needed					

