**Question 17**

**Did you have any other concerns about participating in PIM-COVID that are not listed above?**

**FEEDBACK ON THE PIM-COVID STUDY**

**PIM-COVID is the first UK-wide intensive care trainee-led study. We are interested in feedback on the study design, support provided for local site teams and the individual experiences of those involved.**

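### Study team survey (Appendix 9): three statements on clarity and support sit behind the set-up filter, so only staff involved in set-up can rate them

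*Combined protocol and SAP*

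**What the plan says.** Section 5.2 (Survey of Study Team Members) invites team members at all sites to complete the survey. It serves exploratory objective 5 in Section 3.2, which is feedback from the study team on their involvement.

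In Appendix 9, Question 7 asks "Were you involved with the study set up at your hospital". The routing is "If you answered Yes to Question 7, please proceed to Question 8" and "If you answered No to Question 7, please proceed to Question 9". Question 8 then offers four agreement statements:

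- First, on ease of opening the site: "Setting up the study at my site was easy"
- Second, on clarity of expectations: "It was clear what was expected of the site team"
- Third, on help from the centre: "The site team were well supported by the central study team"
- Fourth, on a route for advice: "I knew who to contact if advice was needed"

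The lead-in to the later feedback section, before Question 18, states: "We are interested in feedback on the study design, support provided for local site teams and the individual experiences of those involved".

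**The concern.** The filter suits the first statement of Question 8, because someone who took no part in set-up cannot say whether it was easy. It does not obviously suit the other three. A person who only recruited patients, collected data or made telephone calls can still have a view on whether expectations were clear, whether central support was adequate and whom to ask for advice. The filter removes those statements for every role.

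At stake is what the survey can say about a topic it names itself. The introduction to Appendix 9 says the results are meant for presentation and publication and will guide the network's later work. If the three ratings come only from set-up staff, they describe that subset and not the whole invited group.

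**Working it through.** The plan gives no figure on this point, so the check is a trace of the survey's routing and content.

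**Step 1: who sees Question 8.** A Yes at Question 7 leads to Question 8 and a No leads to Question 9. No later instruction returns a respondent to Question 8.

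**Step 2: what Question 8 asks.** One of the four statements refers to setting up. The remaining 4 − 1 = 3 name neither set-up nor any other phase. The Site Team section that holds Questions 7 and 8 is introduced as covering both joining the study and its daily running, which is wider than set-up.

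**Step 3: whether another question covers the same ground.**

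- Questions 1 to 6: role, gender, ethnicity, research posts, how the respondent heard of the study, and delegation-log role. No rating of support or clarity.
- Questions 9 to 13: duties, who ran the study locally, weekly time, length of involvement, and reasons for stopping. No rating of support or clarity.
- Questions 14 to 17: motives, hoped-for achievements, barriers, and a free-text question on other concerns. No rating of support or clarity.
- Questions 18 to 21: time commitment, telephone questionnaires, and what was learnt. Question 20 asks whether emotional support matters, not whether support was received, and goes only to those who made telephone questionnaire calls.
- Questions 22 to 24: career intentions, future research, and attitudes to research in training.

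Clarity of expectations, central-team support and knowing whom to contact are therefore each rated once, in Question 8.

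**Step 4: what a respondent who answers No has left.** Question 17 could capture a complaint about support, but Questions 14 to 24 are restricted to junior doctors and allied health professionals. Question 13 has a write-in option, but only as a reason for having stopped. A research nurse or consultant who answers No at Question 7 and is still active has neither.

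**Step 5: whether a bias can be sized.** Let *s* be the share of respondents involved in set-up, *a* the proportion of them agreeing with a statement, and *b* the proportion agreeing among the rest.

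- Reported result: *a*
- Whole-team result: *s·a* + (1 − *s*)·*b*
- Difference: *a* − [*s·a* + (1 − *s*)·*b*] = (1 − *s*)(*a* − *b*)

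The documents give none of *s*, *a* or *b*. If *a* = *b* the difference is zero whatever the share, and its sign is the sign of *a* − *b*. Neither size nor direction can be obtained.

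**The case against.** The strongest reply is that Question 8 is meant as a set-up question throughout. It follows directly from Question 7 and has no stated time frame, and two of its three general statements concern the site team as a unit, so asking the people who opened the site is defensible. That reading cannot be excluded. If it is right, however, support during the rest of the study is rated by nobody, although the lead-in to the feedback section asks for it. The gap changes shape but remains.

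A second reply is that no prespecified result depends on these items. The outcome for objective 5 in Section 3.3 concerns factors influencing involvement, and the topic list in Section 5.2 does not name central-team support, which would at most fall under feedback on involvement. This stands, and it limits how much the point matters.

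A third reply is that the plan contains no analysis or reporting rules for this survey, so nothing says the ratings would be shown without their denominator. This also stands. Labelling would prevent a misreading, but it would not supply the missing ratings.

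Two stronger readings are tempting. A reader might infer that the reported support would be too favourable because set-up staff were closest to the central team. The documents say nothing about relative contact or satisfaction, so this is conjecture. A reader might also infer that the people excluded are those who joined later or rotated through. Question 7 asks about involvement in set-up, not date of joining, so someone present from the start who did other work would also answer No.

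**Conclusion.** The point holds in a limited form. The routing restricts three generally worded statements to staff involved in set-up, no other question rates the same things, and the survey invites all team members and names support for site teams as a topic. Those outside set-up have at most a free-text question open to some roles and, if they have stopped, a write-in reason for stopping.

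The extent is three agreement items in a staff survey serving the last of five exploratory objectives. No patient data, primary outcome or growth-curve analysis is involved. The routing and the absence of a substitute item are facts of the text. That the three statements apply beyond set-up is a reading of their wording, supported by the section introduction but not stated outright. No bias of any given size or direction is claimed. Severity is minor, and the case for acting is that the change is nearly free.

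**What to change.** Keep only the ease-of-set-up statement in Question 8, behind Question 7. Put the other three to every respondent, for example straight after Question 9, which comes before the role restriction that starts at Question 14. Report them overall and by Question 7 answer, with the number responding in each group.

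If responses have already been collected, leave the survey as it is and report the three items explicitly as ratings by set-up staff only, with that denominator.

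The cost is three more tick-box items for respondents not involved in set-up and a small edit to the online form. If the moved statements become a new numbered question, the later skip instructions and the reference to Questions 14 to 24 need renumbering; adding them as a second part of Question 9 avoids this. If the sponsor regards the edit as a change in research activity, it follows the amendment route in Section 7.7.

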**Question 8**

To what extent do you agree with the following?

	Strongly disagree	Disagree	Neither agree nor disagree	Agree	Strongly agree
Setting up the study at my site was easy					
It was clear what was expected of the site team					
The site team were well supported by the central study team					
I knew who to contact if advice was needed					

**Question 9**

**What duties did you undertake during the study?**

*(Please select all that apply)*

- Identifying patients   
 Recruiting participants   
 Data collection and/or participant follow up   
 Supporting other staff on the delegation log   
 Managing site paperwork / screening log

**Question 10**

**Who was involved in the day-to-day running of the study at your site?**

*(Please select all that apply)*

- Trainee PI   
 Research nurse   
 Junior doctor   
 Allied health professional (please specify)   
 \_\_\_\_\_  
 Senior PI   
 Don't know

**Question 11**

**On average how much time did you dedicate to the PIM-COVID study per week?**  
*(Please select one)*

- |              |                          |
|--------------|--------------------------|
| Up to 1 hour |  |
| 1-2 hours    |  |
| 2-4 hours    |  |
| 4+ hours     |  |

**Question 12**

**How long were you actively involved in the PIM-COVID project?**  
*(Please select one)*

- |                             |                          |
|-----------------------------|--------------------------|
| Up to 3 months              |  |
| 3-6 months                  |  |
| 6-12 months                 |  |
| Participation still ongoing |  |

*If 'Participation still ongoing' selected, proceed to Question 14.*

**Question 13**

**If you stopped your involvement in the PIM-COVID study what was the reason?**  
*(Please select all that apply)*

- |  |                          |
|--|--------------------------|
| Moved to a different job or department |  |
| Demands on time or other commitments   |  |
| Did not want to continue               |  |
| Site stopped collecting data           |  |
| Other (please specify)                 |  |

Questions 14-24 are for junior doctors and allied health professionals only (not research nurses or Consultants), as indicated in Question 1.

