##### **Exploratory objectives:**

1. Identify demographic, clinical, physical and/or psychosocial predictors of depression, anxiety and/or trauma symptoms at 3-, 6- and 12-months after ICU discharge in patients being treated for COVID-19 within the ICU.
2. Assess the feasibility of using a self-reported questionnaire to assess anxiety, depression and/or trauma symptoms in patients following ICU admission with COVID-19.
3. Explore the experiences of critical care survivors following COVID-19 infection during their recovery phase, including perceptions about the care received and support available to them, using semi-structured interviews.
4. Assess geographical differences in the availability and structure of follow-up services offered to patients with critical COVID-19 after hospital discharge.
5. Gain feedback from the study team members on their involvement in this trainee-led study.

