#### *Survey of Study Team Members*

Study team members at all PIM-COVID sites will be invited to complete an online survey, which will explore the following:

- Socio-demographic characteristics of study team members
- Previous academic experience
- Feedback on involvement in the PIM-COVID study
- Attitudes towards health research
- Barriers and motivators to contributing to health research
- Future research plans

Questions evaluating participants attitudes, opinions and subjective feedback will be answered using a 5-point Likert scale. (See Appendix 8)

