**Question 19**

**Were you involved in conducting questionnaires with participants over the telephone?**

Yes

No

*If you answered Yes to Question 19 please answer the following question.*

*If you answered No to Question 19 please proceed to Question 21.*

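### The team survey closes its time-commitment and telephone items (Questions 18-20) to research nurses and consultants without a stated reason, and Question 12 cannot record involvement that ended after 12 months

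*Combined protocol and SAP*

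**What the plan says.** Section 3.2 gives exploratory objective 5 as "Gain feedback from the study team members on their involvement in this trainee-led study". Section 5.2, under the survey of study team members, says "Study team members at all PIM-COVID sites will be invited to complete an online survey, which will explore the following". The list that follows includes feedback on involvement, attitudes to research, barriers and motivators, and future plans. Neither place limits a topic to certain roles.

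Appendix 9 then divides the respondents. Questions 1-13 go to everyone. The note after Question 13 reads "Questions 14-24 are for junior doctors and allied health professionals only (not research nurses or Consultants), as indicated in Question 1". The restricted block has three headed parts: motivation and barriers (Questions 14-17), feedback on the study (Questions 18-21) and future research (Questions 22-24). The telephone items lie in the middle part and open with "Were you involved in conducting questionnaires with participants over the telephone".

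Question 12 asks "How long were you actively involved in the PIM-COVID project". Its options are up to 3 months, 3-6 months, 6-12 months, or participation still ongoing. Anyone who ticks the last is sent to Question 14. The study summary in section 1 gives a study duration of 24 months.

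**The concern.** Two things do not fit together.

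- **Who is asked.** The objective and section 5.2 describe feedback from the team. The instrument takes most of its rated feedback from part of the team. The introduction to the feedback part asks about the experiences of those involved in general, yet that part sits inside the role restriction. A report on time burden, or on how staff found the telephone questionnaires, would read as the team's view while leaving out two roles that Question 1 lists as respondents.
- **What Question 12 can record.** A person who stopped after more than 12 months has no true answer. They must pick a wrong duration band, pick ongoing (and so miss Question 13 on why they stopped), or leave the item blank. The skip to Question 14 also carries no role condition. A research nurse or consultant who is still involved is therefore sent into a block that the note closes to them.

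At stake are misclassified or missing survey answers and an unclear denominator for Questions 14-24.

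**Working it through.** The plan gives no figure to reproduce. The check is a count of items in Appendix 9 and a comparison of instructions.

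**Questions closed by the note.** Questions 14 to 24 inclusive: 24 − 14 + 1 = 11. Share: 11/24 = 46%. Open to all roles: 24 − 11 = 13.

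**Rated statements (5-point scale, with a not-applicable box in Question 21).**

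| Question | Subject | Statements | Open to nurses and consultants? |
|---|---|---|---|
| 8 | Set-up and central support | 4 | Yes, if involved in set-up |
| 14 | Reasons for taking part | 7 | No |
| 16 | Barriers | 7 | No |
| 18 | Time commitments | 3 | No |
| 20 | Telephone questionnaires | 3 | No |
| 21 | What was learnt | 6 | No |
| 23 | Future research | 5 | No |
| 24 | Expectations in training | 4 | No |

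Total: 4 + 7 + 7 + 3 + 3 + 6 + 5 + 4 = 39. Closed: 39 − 4 = 35, and 35/39 = 90%.

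**How much of the closure is explained.**

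- Questions 14-17: the introduction to that part says that it looks for factors affecting trainee and allied-health participation. The restriction follows from that purpose. Rated statements: 7 + 7 = 14.
- Questions 21-24: Question 21 asks what the respondent learnt, including about the role of research nurses. The introduction to Questions 22-24 speaks of trainees' plans, and Question 24 concerns UK training schemes. A restriction suits this content. Rated statements: 6 + 5 + 4 = 15.
- Questions 18-20: these ask whether the work fitted around duties and how the telephone questionnaires went. No stated purpose limits them to trainees and allied health professionals. Rated statements: 3 + 3 = 6.

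Sum: 14 + 15 + 6 = 35. The unexplained part is thus 3 questions and 6 of 39 rated statements (15%).

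**Question 12 against the follow-up schedule.** Section 5.2 sends questionnaires at 3, 6 and 12 months after ICU discharge, and an emailed survey link stays open for 1 month. A team member who followed one patient from ICU discharge until the last link closed would be involved for up to 12 + 1 = 13 months. If they then stopped, no option fits. Someone still active at 13 months can tick ongoing, but their duration is not recorded.

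**The two routing instructions.** Question 12 sends every ongoing member past Question 13 to Question 14. The note after Question 13 bars research nurses and consultants from Question 14. For one of them who is still involved, both instructions apply and they disagree. For one who has stopped, only the note applies.

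**The case against.** The best defence is that the restriction is deliberate. Objective 5 calls the study trainee-led, Appendix 9 says that the results will inform the trainee network, and section 5.2 promises that topics will be explored, not that every role will answer every topic. Section 7.8 gives participant contact to junior doctors in conjunction with allied health professionals, who are the groups asked about telephone calls. This stands for Questions 14-17 and 21-24. It does not settle Questions 18-20, because section 5.2 lets any member of the study team take telephone answers and Question 19 already filters out those who made no calls.

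It may also be said that survey software would route by the answer to Question 1. It may, but Appendix 9 does not say which of its two instructions prevails.

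Some stronger readings are tempting, and the documents do not support them:

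- A reader might infer that nurses and consultants can give no feedback. Question 8 depends on set-up involvement, not role ("If you answered Yes to Question 7, please proceed to Question 8"), and includes "The site team were well supported by the central study team". Question 13 asks any role why they stopped, and Questions 9 and 11 take everyone's duties and weekly time.
- A reader might infer that nobody involved beyond 12 months has an answer. Only those who have stopped lack one.
- A reader might infer that a sizeable share of telephone experience is lost. The documents do not say how many calls research nurses made, and naming them as an option in Question 10 does not show who ran the sites.
- A reader might infer harm to the feasibility objective. Section 3.3 lists recruitment, retention, missing data and sample-size quantities, not staff views on calls.

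**Conclusion.** The point holds as a small design fault. Of the 35 rated statements closed to research nurses and consultants, 29 have a purpose or content that suits the restriction. The other 6, with the filter in Question 19, do not. The responses to Questions 18-20 would cover only part of the team named in objective 5 and section 5.2. The omission comes from the routing rule, so it should not be described as self-selection by respondents.

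Question 12 has a definite gap for people who stopped after more than 12 months, takes no duration from those still involved, and contradicts the note. How many people each fault touches cannot be worked out from the documents.

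The conclusion rests on reading objective 5 and section 5.2 as covering all roles, since they state no limit. It affects exploratory objective 5 only. No patient outcome, primary analysis or listed feasibility outcome depends on it.

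**What to change.** 1. Open Questions 18-20 to every role. Keep Questions 14-17 and 21-24 for junior doctors and allied health professionals, and reword the note after Question 13 to match.
2. Split Question 12. Ask everyone for duration in bands that do not overlap: under 3, 3 to under 6, 6 to under 12, and 12 months or more. Then ask separately whether they are still involved, yes or no.
3. Make the skip past Question 13 depend on role. Research nurses and consultants still involved go to Question 18; others still involved go to Question 14. Those who have stopped answer Question 13 and then follow the same split.
4. End the survey for nurses and consultants after Question 20, or at Question 19 if they answer no, because that answer now leads to Question 21.
5. Add a sentence to section 5.2 saying which topics are put to which roles.

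The cost is a change of routing, one divided item and about a minute more for nurses and consultants. With Questions 18-20 open, they could rate 4 + 6 = 10 of 39 statements instead of 4, with Question 8 still depending on set-up involvement and Question 20 on having made calls.
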